The National Cancer Institute's Common Terminology Criteria for Adverse Events (CTCAE) Version 5.0 should be used to assess and grade any AE or SAE, including laboratory abnormalities judged to be clinically significant. Events grade 3 or higher should be collected and documented and reported as indicated. The modified criteria can be found in the study manual. If the experience is not covered in the modified criteria, the guidelines shown in Table 11A below should be used to grade severity. It should be pointed out that the term "severe" is a measure of intensity and that a severe AE is not necessarily serious.

Table 11A. AE Severity Grading

Severity (Toxicity Grade)	Description
Mild (1)	Transient or mild discomfort; no limitation in activity; no medical intervention or therapy required. The subject may be aware of the sign or symptom but tolerates it reasonably well.
Moderate (2)	Mild to moderate limitation in activity, no or minimal medical intervention/therapy required.
Severe (3)	Marked limitation in activity, medical intervention/therapy required, hospitalizations possible.
Life-threatening (4)	The subject is at risk of death due to the adverse experience as it occurred. This does not refer to an experience that hypothetically might have caused death if it were more severe.

AE Relationship to Study Drug

The relationship of an AE to the study drug should be assessed using the following the guidelines in Table 11B.

Table 11B. AE Relationship to Study Drug

Relationship to Drug	Comment
Definitely	Previously known toxicity of agent; or an event that follows a reasonable temporal sequence from administration of the drug; that follows a known or expected response pattern to the suspected drug; that is confirmed by stopping or reducing the dosage of the drug; and that is not explained by any other reasonable hypothesis.

Probably	An event that follows a reasonable temporal sequence from administration of the drug; that follows a known or expected response pattern to the suspected drug; that is confirmed by stopping or reducing the dosage of the drug; and that is unlikely to be explained by the known characteristics of the subject's clinical state or by other interventions.
Possibly	An event that follows a reasonable temporal sequence from administration of the drug; that follows a known or expected response pattern to that suspected drug; but that could readily have been produced by a number of other factors.

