Unrelated	An event that can be determined with certainty to have no relationship to the study drug.

11.2 Serious Adverse Events (SAE) and unanticipated problems involving risk to subjects or others (UPIRSOs)

An SAE is defined as any AE occurring at any dose that results in any of the following outcomes:

- death
- a life-threatening adverse experience
- inpatient hospitalization or prolongation of existing hospitalization⁺⁺
- a persistent or significant disability/incapacity
- a congenital anomaly/birth defect

Other important medical events may also be considered an SAE when, based on appropriate medical judgment, they jeopardize the subject or require intervention to prevent one of the outcomes listed.

⁺⁺ Note that hospitalizations for the following reasons should not be reported as serious adverse events:

- Routine treatment or monitoring of the studied indication, not associated with any deterioration in condition
- Elective or pre-planned treatment for a pre-existing condition that is unrelated to the indication under study and has not worsened since signing the informed consent
- Social reasons and respite care in the absence of any deterioration in the patient's general condition
- Note that treatment on an emergency outpatient basis that does not result in hospital admission and involves an event not fulfilling any of the definitions of a SAE given above is not a serious adverse event

Any serious or immediately life-threatening adverse experience, including those resulting in death, occurring while the subject is receiving study drug, or within 30 days of the subject's last dose of protocol therapy, regardless of the treating

physician's opinion regarding drug relationship, will be reported by telephone and/or e-mail (within 24 hours of the event) to the Study PI and appropriate parties.

Serious Adverse Experience Reporting

Study sites will document all SAEs that occur (whether or not related to study drug) per IRB Guidelines. The collection period for all SAEs will begin after informed consent is obtained and end after procedures for the final study visit have been completed, or thirty days after the subject takes the last dose of study drug, whichever is later.

In accordance with the standard operating procedures and policies of the local Institutional Review Board (IRB)/Independent Ethics Committee (IEC), the site investigator will report SAEs to the IRB/IEC.

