SAEs (as well as reports of drug exposure during pregnancy and reports of study drug misuse or abuse) will be forwarded to Novartis within one business day of Study PI becoming aware.

The principal investigator has the obligation to report all serious adverse events to the FDA (if applicable), IRB, and Novartis Pharmaceuticals Drug Safety and Epidemiology Department (DS&E)

All events reported to the FDA by the investigator are to be filed utilizing the Form FDA 3500A (MedWatch Form), if applicable

To ensure patient safety, every SAE, regardless of suspected causality, occurring after the patient has provided informed consent and until at least 30 days after the patient has stopped study treatment must be reported to Novartis within 24 hours of learning of its occurrence. Information about all SAEs is collected and recorded on a Serious Adverse Event Report Form. The investigator must assess and record the relationship of each SAE to each specific study treatment (if there is more than one study treatment), complete the SAE Report Form in English, and send the completed, signed form along with the Novartis provided fax cover sheet to the Novartis Oncology Drug Safety and Epidemiology (DS&E) department by fax ([contact]) within 24 hours.

Any additional information for the SAE including complications, progression of the initial SAE, and recurrent episodes must be reported as follow-up to the original episode within 24 hours of the investigator receiving the follow-up information. An SAE occurring at a different time interval or otherwise considered completely unrelated to a previously reported one should be reported separately as a new event.

Any SAEs experienced after the 30 day safety evaluation follow-up period should only be reported to Novartis if the investigator suspects a causal relationship to the study treatment.

Follow-up information is submitted in the same way as the original SAE Report. Each re-occurrence, complication, or progression of the original event should be reported as a follow-up to that event regardless of when it occurs. The follow-up information should describe whether the event has resolved or continues, if and how it was treated, whether the blind was broken or not, and whether the patient continued or withdrew from study participation.

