If the SAE is not previously documented in the Investigator's Brochure or Package Insert (new occurrence) and is thought to be related to the Novartis study treatment, an oncology Novartis Drug Safety and Epidemiology (DS&E) department associate may urgently require further information from the investigator for Health Authority reporting. Novartis may need to issue an Investigator Notification (IN), to inform all investigators involved in any study with the same drug that this SAE has been reported. Suspected Unexpected Serious Adverse Reactions (SUSARs) will be collected and reported to the competent authorities and relevant ethics committees in accordance with Directive 2001/20/EC or as per national regulatory requirements in participating countries.

To ensure patient safety, each pregnancy occurring while the patient is on study treatment must be reported to Novartis within 24 hours of learning of its occurrence. The pregnancy should be followed up to determine outcome, including spontaneous or voluntary termination, details of the birth, and the presence or absence of any birth defects, congenital abnormalities, or maternal and/or newborn complications. Pregnancy should be reported by the investigator to the Novartis Oncology Drug Safety and Epidemiology Department (DS&E) by fax ([contact]). Pregnancy follow-up should include an assessment of the possible relationship to the [investigational/study treatment] any pregnancy outcome. Any SAE experienced during pregnancy must be reported on the SAE Report Form.

Pregnancy outcomes must be collected for the female partners of any males who took study treatment in this study. Consent to report information regarding these pregnancy outcomes should be obtained from the mother.

All SAEs, regardless of causality, will be reported to:

- Site Principal Investigator
- Site IRB of Record (per institutional policy)
- Coordinating Center within 24 hours of a member of the research team becoming aware of the event.

SAEs should be recorded on the appropriate SAE Form. The SAE Form, along with any relevant information or documentation, must be submitted to the Site Principal Investigator for review and signature then reported via email to the Coordinating Center per contact information in Manual of Operations.

Protocol Defined Important Medical Findings Requiring Real Time Reporting

- Grade 5 hemorrhage
- Thromboembolic event
- Death

- Malignancy

UPIRSOs

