An UPIRSO is defined as an event that meets all three of the following criteria:

Unexpected (in terms of the nature, severity or frequency) given

- The research procedures that are described in the protocol-related documents, such as the IRB-approved research protocol and informed consent document; and
- The characteristics of the subject population being studied.
- Suggests that the research places subjects or others at a greater risk of harm (including physical, psychological, economic or social harm) than was previously known or acknowledged.

“Related to the research procedures”: An event is “related to the research procedures” if in the opinion of the principal investigator, it was more likely than not to be caused by the research procedures or if it is more likely than not that the event affects the rights and welfare of current participants.

All UPIRSOs will be reported to:

- Site Principal Investigator (immediately upon member of research team becoming aware)
- Site IRB of Record (in accordance with site’s institutional policy)
- Coordinating Center as soon as possible, but no more than 24 hours from the time a member of the research team is aware of the event.

UPIRSOs should be recorded on the appropriate SAE Form. The SAE Form, along with any relevant information or documentation, must be submitted to the Site Principal Investigator for review and signature then reported via email to the Coordinating Center (Boston Children’s Hospital) and Baylor College of Medicine as per manual of operations. IRB approval/acknowledgment should also be provided to the coordinating center upon site’s receipt.

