To monitor for early evidence of efficacy or lack of efficacy (futility), we will perform group sequential analyses for a total of three “looks” at the data. Power calculations were performed using PASS 14 (NCSS, LLC. Kaysville, Utah, USA). We will conduct two interim analyses using a two-sided Cochran-Mantel-Haenszel test to compare the proportion of platelet responders between the two treatment arms, after 33% and after 67% of randomized patients are accrued. If the trial has not been terminated due to efficacy or futility, the third and final analysis will be conducted after accrual of all randomized patients at the end of the trial. We used the O’Brien-Fleming spending function to determine the monitoring boundaries for these three group sequential tests (Table 16A, Figure 1). For interim analysis 1, significant evidence that the experimental drug is more efficacious than the standard of care will have been provided if we observe a z-test statistic ≥ 3.71 . Significant evidence that the experimental drug is less efficacious than the standard therapy will have been provided if $z \leq -3.71$. For

interim analysis 2, significant evidence that the experimental drug is efficacious or not will have been provided if $z \geq 2.51$ or ≤ -2.51 , respectively. For the final analysis, significant evidence of the efficacy of the experimental drug will have been provided if $z \geq 1.99302$. The members of the study committee will remain masked to the results of the interim analyses. Because the results of this trial will set a new standard of care for this patient population, an independent Data Safety Monitoring Board (DSMB) will make a non-binding recommendation if/when it is appropriate to close the trial early on the basis of the statistical evidence.

[figure not shown]
Table 16A: Interim analysis monitoring boundaries and operating characteristics

Look	Proportion accrued	Lower Bndry	Upper Bndry	Nominal Alpha	Alpha Spent	Total Alpha	Power Spent	Total Power
1	0.33	-3.7103	3.7103	0.0002	0.0002	0.0002	0.02009	0.0201
2	0.67	-2.51142	2.51142	0.012	0.0119	0.0121	0.41425	0.4343
3	1	-1.99302	1.99302	0.0463	0.0379	0.05	0.38006	0.8144

Definitions:

- Nominal alpha: the significance level to be used for a single, standalone test at each interim test.
- Alpha spent: the amount of alpha spent by this interim test.
- Total alpha: the total amount of alpha that is used up to and including the current test.

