- Power spent: the probability that the significance is found and the trial is stopped, given the alternative hypothesis (also called “exit probabilities”).
- Total power: these are the cumulative power values.

Figure 1. O’Brien-Fleming interim monitoring efficacy (red) and futility (green) boundaries for the rate of sustained of platelet response, comparing the eltrombopag arm to the standard of care arm using a two-sided Cochran-Mantel-Haenszel test

Interim analyses for safety

AEs and SAEs will also be reviewed at interim analysis 1 and 2. If any toxic deaths, or 2 intracranial hemorrhages, or 2 unprovoked thromboses are found at the first interim analysis, study will be temporarily halted to accrual for further evaluation.

f. Sample Size and Study Duration

Power Calculations for the Primary Objective

147 “informative” (as defined below) patients, randomized 2:1 to the experimental treatment arm and standard treatment arm, will be required to provide 81.4% power to detect an absolute difference of 25% in the proportion of patients who are platelet responders, assuming the response rate is 75% in the experimental treatment arm and 50% in the standard treatment arm, using a one-sided Cochran-Mantel-Haenszel (CMH) test and a type I error rate of 0.025. In order to provide at least 147 informative patients, up to 162 patients will be enrolled and randomized.

The first time point at which the primary endpoint, platelet response, will be assessed is 5 weeks after enrollment. A small number of patients, approximately

9%, are anticipated to withdraw from the study (i.e., withdraw from protocol therapy AND data submission) prior to the 5-week platelet assessment. It is reasonable to assume that the study withdrawal rate will be similar across the treatment arms. These patients are non-informative for the primary objective to assess the efficacy of eltrombopag; such patients dilute the treatment effect and as a result the power is diminished. These “non-informative” patients will be classified as non-responders and included in the ITT analysis. We will assume that 9% of randomized patients, a conservatively high estimate, will be non-informative. To account for the diluting effect the non-informative patients have on the comparison of response rates, we plan to enroll and randomize up to an additional 15 patients (~9%).

Total sample size and study duration

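### Section 16.e ties its safety halt on accrual to interim analysis 1 only, so a qualifying event before that look pauses nothing until then and a toxic death after it triggers no pause

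*Combined protocol and SAP*

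**What the plan says.** Section 16.e first sets the occasions for safety review: "AEs and SAEs will also be reviewed at interim analysis 1 and 2". The efficacy part of the same section fixes when those analyses occur: "after 33% and after 67% of randomized patients are accrued". The sentence after the review statement then gives the only study-level safety halt in the documents. Its criteria are any toxic death, two intracranial hemorrhages or two unprovoked thromboses. Its scope is the first look: if "or 2 unprovoked thromboses are found at the first interim analysis, study will be temporarily halted to accrual for further evaluation".

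Section 14 describes two DSMC reviews under a charter still to be established, and sends the reader back to the statistical section for their timing and content.

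Section 11.2 moves the relevant information quickly. Serious or immediately life-threatening events on study drug, or within 30 days of the last dose, "will be reported by telephone and/or e-mail (within 24 hours of the event) to the Study PI and appropriate parties". Under the title "Protocol Defined Important Medical Findings Requiring Real Time Reporting" it lists Grade 5 hemorrhage, thromboembolic events, death and malignancy. UPIRSOs go to the "Coordinating Center as soon as possible, but no more than 24 hours from the time a member of the research team is aware". No action on accrual is attached to any of these reports.

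**The concern.** Two adjacent sentences differ in scope, and no reason is given: review takes place at both looks, but the trigger operates at one. In a pediatric trial, the protocol treats a single toxic death as sufficient reason to pause accrual when it is found at look 1. Yet a site that reported such a death in the second month would set off no pause for most of a year. The same death in the second year would set off none. In both cases the sponsor would hold the report within about a day. A pause would then depend on someone's discretion rather than on the rule the protocol has written down, which is what a pre-specified trigger is meant to avoid.

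**Working it through.** **1. Is the missing trigger supplied elsewhere?**

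- Section 8.2.2.5 stops eltrombopag in an individual patient after specified events. It does not address accrual.
- Section 11.2 requires reporting only.
- Sections 12.1 and 12.2 cover discontinuation and withdrawal of individual patients.
- Section 14 refers back to Section 16.
- Section 18.a permits an immediate-hazard amendment but sets no threshold.

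No other study-level halt was found. Section 16.e states no operating characteristic for the safety rule, so there is no planned figure to reproduce.

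**2. When does look 1 fall?** Inputs are 162 patients, a look at 33% (Section 16.e), and 45 patients a year or about 3 years of accrual (Section 16.f). The two pace statements differ (162/45 = 3.6 years), so both are used.

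- Patients at look 1: 0.33 × 162 = 53.5, about 54.
- At 45/12 = 3.75 a month: 53.5/3.75 = 14.3 months.
- At 162/36 = 4.5 a month: 53.5/4.5 = 11.9 months.
- Enrolling afterwards: 162 − 54 = 108, or 67%.

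The primary endpoint runs to week 12. If the look waits 12 weeks (2.77 months) for the last patient's endpoint, which is an assumption, 3.75 × 17.0 = 64 or 4.5 × 14.65 = 66 patients are enrolled by then. About 96 to 98 (60%) follow.

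**3. How long is the delay before look 1?** Assume constant risk over 12 months on study and uniform accrual. With T the time of the look in months, the number at risk at month s is proportional to min(s, 12), and the mean wait is ∫(T − s)·min(s,12) ds / ∫min(s,12) ds.

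- T = 11.9: T/3 = 4.0 months.
- T = 14.3: 481/99.1 = 4.9 months.
- If the look waits 12 weeks (T = 14.65 or 17.0): about 5 to 6 months.

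**4. How many more pauses would the fix cause?** With r patients a month, patient-years at time T are r·T²/24 up to month 12 and r·(T − 6) after it.

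| Pace | Patient-years at look 1 | Patient-years at end of accrual |
|---|---|---|
| 3.75/month | 3.75 × 8.26 = 31.0 | 3.75 × 37.2 = 139.5 |
| 4.5/month | 4.5 × 141.1/24 = 26.5 | 4.5 × 30 = 135.0 |

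The documents give no usable event rate. Section 2.3 reports no thromboembolic events in two earlier pediatric trials, without a denominator. All rates below are therefore assumptions per patient-year, applied to both arms.

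Toxic death, P1 = 1 − exp(−rate × patient-years):

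- 0.1%: 2.6–3.0% under the current rule, 12.6–13.0% if carried through accrual.
- 0.05%: 1.3–1.5%, rising to 6.5–6.7%.
- 0.2%: 5.2–6.0%, rising to 23.7–24.3%.

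Pause for any reason, with toxic death at 0.1%, each count-of-two event at rate p, and independence. Here m = p × patient-years at look 1, P2 = 1 − e^(−m)(1 + m), and the result is 1 − (1 − P2)² × (1 − P1). P1 runs to look 1 under the current rule and to the end of accrual under the fix.

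| p | Current rule | With the fix |
|---|---|---|
| 0.5% | 4–5% | 14–15% |
| 1% | 8–11% | 18–20% |
| 2% | 21–26% | 29–34% |

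Worked case at p = 1% and 3.75 a month: m = 0.310 and P2 = 3.9%, so 1 − 0.961² × 0.970 = 10.5% now, and 1 − 0.961² × 0.870 = 19.7% with the fix.

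**The case against.** The best defence is that an automatic rule for early experience, followed by DSMC judgement, is a recognisable design. For the counts of two this has force. Two events are 2/54 = 3.7% of patients at look 1 but 2/162 = 1.2% of the full trial, so the same count means something different later. It does not carry over to toxic death, where one event suffices and there is no rate to dilute.

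The second defence is that the gap is narrow. Serious events are reported within 24 hours, eltrombopag is stopped in individual patients after specified thrombotic events, events are reviewed again at look 2, and the DSMC may act at any time under a charter not among the documents. All of this stands. A reader might infer that safety goes unmonitored outside look 1, or that an event before look 1 is lost. The documents support neither: oversight continues, and an earlier event still counts at look 1, so its effect is delayed. The charter defence is only partial, because Section 14 points back to Section 16 for the content of the reviews.

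A reader might also infer that causality is not assessed, leaving a toxic death unidentifiable. That is not so. Section 11.1 says "The relationship of an AE to the study drug should be assessed using the following the guidelines in Table 11B", and for serious events Section 11.2 adds "The investigator must assess and record the relationship of each SAE to each specific study treatment". What is missing is which level counts as toxic, and what unprovoked means. Those are matters of wording.

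On cost, treating all 54 patients as having a full year of follow-up would put the chance of any pause at 24% rising to 31% at p = 1%. That overstates both levels and understates the proportional increase, which is roughly a doubling.

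**Conclusion.** The point holds as a reading of Section 16.e and is limited to the automatic trigger. Followed exactly, the plan lets accrual continue after a reported toxic death until look 1, and sets no trigger for one after it. About 60 to 67% of patients enroll after the only look with a trigger, depending on whether that look waits for endpoints. For a toxic death before look 1, the mean delay is about 4 to 5 months, longer if the look waits.

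The textual finding depends on no assumed rate. The delay rests on constant risk and uniform accrual, and the pause probabilities also rest on the assumed event rates and independence. The documents do not support the stronger conclusion that the counts of two must continue unchanged after look 1. The first-look limit may also be intended, in which case the protocol should say so.

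**What to change.** Amend Section 16.e, using the thresholds already there:

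- **(a)** Before look 1, the existing criteria act as soon as the expedited reports show they are met, with accrual paused and the DSMC convened.
- **(b)** The any-toxic-death criterion applies throughout accrual, including at look 2.

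Alternatively, if the DSMC charter already provides this or the first-look limit is intended, state that in Section 16.e and cite the charter. Whether the counts of two continue after look 1, and if so whether they accumulate or restart, is for the sponsor and DSMC to decide. The same edit could link toxic to a level of Table 11B and define unprovoked.

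The cost is a short paragraph, matching charter text and possibly some unscheduled DSMC calls. Part (a) adds almost no pauses, because it applies the same counts to the same patients sooner. Part (b) accounts for the increase in temporary pauses shown in the working. Alpha, power, sample size and treatment of individual patients do not change.

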4 STUDY DESIGN

This is a prospective, open label, randomized, two-arm, multi-center Phase 3 trial. Patients with newly diagnosed ITP are randomized 2:1 to receive the experimental treatment, eltrombopag, or investigator's choice of 3 standard therapies. The primary objective is to determine if the proportion of patients with platelet response is significantly greater in patients treated with eltrombopag compared to those treated with standard therapies.

Randomization at study enrollment will be stratified by the two factors described below, using a block size of 3.

- a) Age at enrollment
- b) Whether the patient has received a first-line treatment (as defined in inclusion criteria):
 - **1) Upfront treatment:** Patients *within 10 days* of ITP diagnosis who have not received previous treatment
OR
 - **2) Treatment failure:** Patients who have failed standard management (observation or treatment with one or more first-line standard agents)

Table 4A: Stratification strata and stratum-specific patient enrollment limits

Stratum	Patient Age at Enrollment	Patient Up-front Treatment Status	Maximum Number of Patients Enrolled
1	1 – <6	Requires up-front treatment	27
2	1 – <6	Failed up-front treatment	27
3	6 – <12	Requires up-front treatment	27
4	6 – <12	Failed up-front treatment	27
5	12 – <18	Requires up-front treatment	27
6	12 – <18	Failed up-front treatment	27

Patients randomized to the eltrombopag arm will be eligible to continue the treatment throughout the 1-year duration of study participation, with guidelines given for dose adjustments.

A total of up to 162 patients will be enrolled. The required sample size is 147 “informative” patients (as defined below), with 104 (estimated 98 informative) in the experimental treatment arm and 52 (estimated 49 informative) in the standard treatment arm. A conservatively high estimate of 9% of patients are anticipated to withdraw from the study prior to the 5-week platelet assessment; these patients will be classified as non-responders, and will make a non-informative contribution to the analysis response rate for the primary objective. Therefore, to obtain at least 147 informative randomized patients, we plan to enroll and randomize up to an additional 15 patients (9 and 6 for the eltrombopag and standard treatment arms, respectively) for a total of 162.

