To address the primary objective, we will first test for normality of the distribution of the proportion of platelet responders. If the assumption of normality is upheld, a one-sided Cochran-Mantel-Haenszel (CMH) test, at alpha=0.025, will be used to compare the proportion of platelet responders between the two arms. If the normality assumption is violated, then a one-sided Fisher's exact test will be used. The monitoring boundaries and levels of significance for the interim and final analyses of the primary endpoint are detailed in Table 16A. If a monitoring boundary is crossed in an interim analysis, an independent Data Safety Monitoring Board (DSMB) will make a non-binding recommendation regarding trial conduct or potential closure. In the final analysis, we will reject the null hypothesis if the upper (efficacy) boundary z-value of 1.99302 is crossed; in that case, it will be reasonable to conclude that the rate of platelet response is significantly greater in patients treated with eltrombopag than standard first-line treatments. Otherwise, we will conclude that there is insufficient evidence to support superiority of eltrombopag over standard first-line treatments. All randomized patients will be analyzed in the ITT analysis.

Selection of platelet measurements for the determination of platelet response.

All platelet counts will be reported, and the four measurements closest in time to Weeks 6, 8, 10, and 12 will be selected for the determination of the primary endpoint. Within a sliding one-week window, only one measurement can be selected. Patients who have <3 platelet measurements due to missing data will be classified as non-responders.

c. Analysis of Secondary Endpoints

Analyses of all secondary endpoints will be performed in the subset of evaluable patients. To determine the effects of missing data, sensitivity analyses will be performed using two approaches: a) assuming missing at random; and, b) assuming missing not at random. For each secondary endpoint, the assumption of normality will be tested. If violated for binary endpoints, a Fisher's exact test will be used. If violated for continuous endpoints, a Wilcoxon rank-sum test will be used.

To address secondary objective 3.2.1, the Cochran-Mantel-Haenszel test will be used to compare the proportion of patients with poor WHO Bleeding Score and poor Modified Buchanan Score between the two arms.

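### Section 16.f gives 81.4% power for 147 informative patients but none for the 162-patient ITT analysis, which has about 79% (74% with continuity correction) at the plan's 9% withdrawal; Section 4's arm sizes and the 3-year accrual do not fit 162

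*Combined protocol and SAP*

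**What the plan says.** - **Power.** Section 16.f states that 147 informative patients, randomized 2:1, "will be required to provide 81.4% power to detect an absolute difference of 25% in the proportion of patients who are platelet responders", at 75% versus 50% and one-sided alpha 0.025. Table 16A carries the same total as 0.8144. On software, Section 16.e says "Power calculations were performed using PASS 14", without settings.
- **Withdrawal.** Section 16.f: "We will assume that 9% of randomized patients, a conservatively high estimate, will be non-informative". It says of them that "such patients dilute the treatment effect and as a result the power is diminished", and that these "patients will be classified as non-responders and included in the ITT analysis". The rate is taken to be similar in the two arms.
- **Remedy.** "To account for the diluting effect the non-informative patients have on the comparison of response rates", up to 15 further patients are enrolled, for a total of 162 (108 and 54). All randomized patients enter the primary analysis.
- **Arm sizes in Section 4.** The requirement is 147 informative patients, "with 104 (estimated 98 informative) in the experimental treatment arm and 52 (estimated 49 informative) in the standard treatment arm". It then adds 15 patients, split 9 and 6, for a total of 162.
- **Accrual.** Section 16.f expects 45 patients per year, about 3 years of accrual and 4 years in total.

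**The concern.** Dividing 147 by 0.91 gives the right enrollment when withdrawals leave the analysis. Here they stay in both denominators as non-responders, so the difference being tested shrinks as well. The plan acknowledges the dilution and presents the 15 extra patients as the answer to it, but never computes power for the diluted comparison.

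Two further sets of figures do not fit. Sections 4 and 16.f give different arm sizes, and imply different withdrawal rates, for one trial. The accrual period is too short for the enrollment at the stated rate. At stake is whether the sponsor, the monitoring committee and the sites are working from the correct power, arm sizes and end date.

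**Working it through.** **Method.** Three looks at information 1/3, 2/3 and 1, with the Table 16A bounds 3.7103, 2.51142 and 1.99302, by numerical integration. Under the null hypothesis these bounds give a one-sided error of 0.0250. The drift is (p1 − p2)/SE, with SE pooled, √[p̄(1 − p̄)(1/n1 + 1/n2)], or unpooled, √[p1(1 − p1)/n1 + p2(1 − p2)/n2]. The continuity-corrected version subtracts ½(1/n1 + 1/n2) from the difference. The CMH stratification is ignored.

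**1. The plan's own 81.4%.** Table 16A's total power of 0.8144 needs a drift of 2.872, with exit probabilities 0.0201, 0.4142 and 0.3801 (table: 0.02009, 0.41425, 0.38006).

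For 98:49 at 0.75 versus 0.50, p̄ = 98/147 = 0.6667, pooled SE = 0.0825 and drift = 0.25/0.0825 = 3.031.

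| 98:49, undiluted | Drift | Power |
|---|---|---|
| Pooled | 3.031 | 85.4% |
| Unpooled | 2.985 | 84.3% |
| Pooled, corrected | 2.846 | 80.7% |
| Unpooled, corrected | 2.802 | 79.5% |

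The pooled corrected version is close, but none of the four reproduces 2.872. Two other designs do, both pooled and uncorrected:

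- Section 4's 104:52 with 98 and 49 informative. The rates are 0.75 × 98/104 = 0.7067 and 0.50 × 49/52 = 0.4712, the drift is 2.870 and the power 81.4%. This implies 5.8% withdrawal; at 9% the same design has 77.8%.
- 88:44 undiluted (132 patients): drift 2.872, power 81.4%. The documents never mention 132.

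The documents do not show which design, if either, was used.

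**2. Power of the planned ITT analysis.** With 9% scored as non-responders in each arm, the rates are 0.91 × 0.75 = 0.6825 and 0.91 × 0.50 = 0.455, a difference of 0.2275. For 108:54, p̄ = (73.71 + 24.57)/162 = 0.6067, pooled SE = 0.0814 and drift = 2.794.

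| 108:54, 9% withdrawal | Drift | Power | Change from 98:49 undiluted |
|---|---|---|---|
| Pooled | 2.794 | 79.3% | 85.4% to 79.3% |
| Unpooled | 2.801 | 79.5% | 84.3% to 79.5% |
| Pooled, corrected | 2.624 | 74.1% | 80.7% to 74.1% |
| Unpooled, corrected | 2.630 | 74.3% | 79.5% to 74.3% |

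**3. Sensitivity to withdrawal (108:54, pooled).**

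| Withdrawal | Uncorrected | Corrected |
|---|---|---|
| 6% | 82.6% | 77.8% |
| 7% | 81.5% | 76.6% |
| 8% | 80.4% | 75.3% |
| 9% | 79.3% | 74.1% |

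Power reaches 80% at 8.4% withdrawal or below uncorrected, and at 4.2% or below corrected.

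**4. Fisher fallback.** Section 16.b switches to Fisher's exact test on this condition: "If the normality assumption is violated, then a one-sided". A fixed-sample exact calculation at the final nominal one-sided level of 0.0231 gives 73.1% for 108:54 at 9%, and 79.9% for 98:49 undiluted. These are not group-sequential figures and should not be read against Table 16A.

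**5. Arm sizes.**
- 104 + 52 = 156, not 162.
- (6 + 3)/156 = 5.8% loss, not 9%.
- Adding 9 and 6 to 98 and 49 gives 107 and 55, not 108 and 54.
- Table 4A has six strata of 27. Each holds nine blocks of 3, so 18:9 per stratum and 108:54 overall. Hence 98 + 10 = 108 and 49 + 5 = 54.

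**6. Accrual.** 162/45 = 3.6 years (162/3.7 = 43.8 months) and 147/45 = 3.3 years. Three years at 45 gives 135 patients. With one year of follow-up, the total is about 4.6 years.

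**The case against.** - **The plan names no 80% target, and 9% is its own upper estimate.** Correct. The fair benchmark is 81.4%. Uncorrected, the loss against it is about 2 points, the shortfall below 80% is under one point, and at 7% withdrawal the stated figure is recovered. But 9% is the rate on which the plan bases its enlargement to 162.
- **The 74% rests on a continuity correction that the documents do not mention.** This also stands; it is an assumption. Uncorrected power at 9% is still below 81.4%.
- **If 81.4% came from 104:52 with 98 and 49 informative, it already is a diluted ITT power.** The fault would then be a withdrawal rate of 5.8% in place of 9%, and the 5-to-7-point loss would start from a baseline that the sponsor never used. This cannot be excluded. But Section 16.f ties the figure to 147 informative patients and to 9%, and power for 162 at 9% is lower on either reading.
- **Taken literally, 107:55 with 98 and 49 informative gives about 84% uncorrected and 80% corrected.** True, but it implies 8.4% withdrawal (9/107) in one arm and 10.9% (6/55) in the other, whereas Section 16.f assumes similar rates.

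None of these points touches the arm-size or accrual arithmetic.

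**Conclusion.** The concern holds. No power is stated for the analysis that will be run. At the plan's 9% withdrawal, that power is 79.3% to 79.5% uncorrected or 74.1% to 74.3% corrected, below the stated 81.4% in every variant. Comparing like with like, moving from 147 undiluted to 162 ITT costs about 5 to 7 points. The 15 extra patients do not make up for the dilution they are said to cover.

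These figures assume 75% versus 50%, equal withdrawal in the two arms, the full 162 patients and an unstratified test. Since 162 is a ceiling, fewer patients would lower the power further. The origin of 81.4% remains open.

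The contradictions in Section 4 and the accrual shortfall (3.6 years against about 3, and 4.6 in total against 4) follow from the plan's own numbers. All of this should be corrected, but none of it invalidates the design.

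**What to change.** - **Section 16.f, power:** rerun the sponsor's software for 108:54 at 68.25% versus 45.5% and state that ITT power (expected 74% to 79%, depending on settings). Name the variance and continuity-correction settings, and give power at 6%, 7%, 8% and 9% withdrawal.
- **Section 16.f, origin:** say which design and withdrawal rate produced 81.4%.
- **Table 16A:** replace the power columns with output from the same run.
- **Section 4:** replace 104 and 52 with 108 and 54, and the 9 and 6 extra patients with 10 and 5, in line with Section 16.f and Table 4A.
- **Accrual:** restate as about 3.6 years, and total duration as about 4.6 years, for 162 patients.

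The cost is one software rerun and restated figures in Sections 4 and 16. The stated power becomes less favorable and the stated duration longer. No extra patients and no change to test, alpha or boundaries are needed.
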